2.6.2 Statistical hypothesis, model, and method of analysis

Analyses of secondary efficacy variables 1 and 8 - 21 will be similar to the primary analysis of primary efficacy variable 1 (using MMRM, but with a two-sided 95% confidence interval for all applicable estimates).

Secondary efficacy variable 2, 3, and 23 will be analyzed using a linear model with treatment, baseline LDL-C, and [REDACTED] as explanatory variables. Least-squares mean of each treatment group, least-squares mean treatment difference, 95% confidence interval for the treatment difference, and p-value based on the fitted model will be reported. Variables 2 and 3 are calculated by averaging the observed post-baseline values (change or percent change) for each participant across analysis visits Day 90, Day 180, Day 270, and Day 330. The outcome value for variable 23 is a proportion that is calculated for each participant with total number of study days equal to duration on study as defined in Section 2.3.1.

Secondary efficacy variables 4 - 7 will be analyzed at each applicable post-baseline visit using a logistic regression model with treatment, baseline LDL-C, and [REDACTED] as explanatory variables (Stokes et al 2012). The odds ratio, 95% confidence intervals for the odds ratio, and p-value based on the fitted model will be reported. Missing data will be imputed using “non-responder” (i.e., “negative” outcome) imputation.

Secondary efficacy variable 22 will be analyzed at each post-baseline visit using a proportional odds model with treatment, baseline LDL-C, and [REDACTED] as explanatory variables (Stokes et al 2012). The odds ratios, 95% confidence intervals for the odds ratios, and p-values based on the fitted model will be reported. Missing data will not be imputed.

Visit-to-visit LDL-C variability from Day 90 until Day 330 will be reported, using various measures of variability (standard deviation and coefficient of variation) (Bangalore et al 2015).

Analyses of secondary efficacy variables will be based on the FAS.

2.6.3 Handling of missing values

For the analysis of secondary efficacy variables 1 and 8-21, the MMRM implicitly imputes missing data under a missing at random assumption.

For the analysis of secondary efficacy variables 4 – 7, participants with missing data will be imputed using “non-responder” (i.e., “negative” outcome) imputation.

For the analysis of secondary efficacy variables 2, 3, 22 and 23, missing data will not be imputed.

2.6.4 Sensitivity analyses

Not applicable.

2.6.5 Supplementary analyses

Secondary efficacy variables 2 and 3 will be analyzed using MMRM similar to the analysis of primary efficacy variable 1 and secondary efficacy variable 1, respectively. A linear combination of the estimated means will be used to estimate the time-adjusted percent change and absolute change from baseline in LDL-C, where “time-adjusted” refers to the estimated average from Day 90 through Day 330. Least-squares mean of each treatment group, least-squares mean treatment difference, 95% confidence interval for the treatment difference, and p-value based on the fitted model will be reported.

2.7 Safety analyses

All safety analyses will be performed on the Safety Set.

2.7.1 Adverse events (AEs)

The Medical Dictionary for Regulatory Activities (MedDRA) dictionary will be used for coding AEs, and up-versioning will be applied during study. The final MedDRA version used in this study was v26.1. An AE (classified as preferred term) occurring during the treatment period will be counted as a treatment-emergent AE (TEAE) either if it is not present at Day 1 before treatment or if it is present before treatment but increased in severity during the treatment period.

The following summary tables will be presented:

- Overall Summary of TEAEs
- TEAEs by System Organ Class (SOC) and Preferred Term (PT)
- TEAEs by PT
- Common TEAEs ($\geq 3\%$ within either treatment group) by PT
- TEAEs by SOC, PT, and Severity
- TEAEs by SOC, PT, and Relationship to Study Treatment
- Related TEAEs by SOC, PT, and Severity
- Treatment Emergent Serious AEs (TESAEs) by SOC and PT
- TESAEs by PT
- TESAEs by SOC, PT, and Severity
- TESAEs by SOC, PT, and Relationship to Study Treatment
- Related TESAEs by SOC, PT, and Severity
- TEAEs Leading to Withdrawal of Study Treatment by SOC and PT
- TEAEs with a Fatal Outcome by SOC and PT

If more than one event occurred with the same PT for the same participant, the participant will be counted only once for that PT using the most severe or related occurrence for the summary by severity, or relationship to study drug, respectively.

Missing severity and relationship will not be imputed and will be identified as ‘missing’ in the tables.

For common (3% within either treatment group) TEAEs, serious TEAEs and TEAEs leading to withdrawal of study treatment, risk ratios along with 95% confidence intervals will be presented to compare treatment groups with respect to risk.

For tables presented by SOC and PT, system organ classes are sorted alphabetically and within each system organ class, the preferred terms are sorted in descending order of total frequency.

For tables presented by PT, preferred terms are sorted in descending order of total frequency.

Listings will be presented for participants with SAEs and AEs leading to discontinuation of study treatment.

2.7.1.1 Adverse events of special interest / grouping of AEs

TESAEs and TEAEs of special interest will be tabulated.

SAEs of special interest include:

1. Hepatotoxicity
2. Renal events

AEs of special interest include:

1. TEAE at the injection site
 - TEAE identified as being an AE at the injection site on the AE CRF page
 - Injection site reaction (HLT)
2. Hepatotoxicity
 - Drug related hepatic disorders - comprehensive search (SMQ, broad and narrow)
3. Renal events
 - Acute renal failure (SMQ, broad and narrow)
4. New-onset/worsening of diabetes
 - Hyperglycemia/new-onset diabetes mellitus (SMQ, narrow)
 - Diabetic Complications (HLGT)
 - Diabetes Mellitus (HLT)
 - Carbohydrate tolerance analyses (HLT), excluding PT “Blood glucose decreased”
5. Hypersensitivity
 - Hypersensitivity (SMQ, broad and narrow) excluding
 - PTs ‘infusion site %’ (e.g., ‘infusion site dermatitis’, ‘infusion site eczema’, ‘infusion site hypersensitivity’, ‘infusion site rash’, ‘infusion site urticaria’, ‘infusion site vasculitis) and

- PTs 'injection site %' (e.g., 'injection site dermatitis', 'injection site eczema', 'injection site hypersensitivity', 'injection site rash', 'injection site urticaria' and 'injection site vasculitis')

2.7.2 Deaths

Listings will be presented for participants with SAEs/AEs leading to a death.

2.7.3 Laboratory data

Laboratory values will be summarized by treatment group, including the observed value, changes and percent changes from baseline at each analysis visit (including Day 330/Last Visit). Fasting glucose parameter, when used in any analysis, will require the lab sample to be taken while fasting. Glucose values recorded under non-fasting conditions will not be used.

A shift analysis using the normal range (except for eGFR [REDACTED]) will be done which counts the number of participants with a low, normal or high value at baseline and a low, normal or high value post baseline.

The following ranges will be used for estimated Glomerular Filtration Rate (eGFR) [REDACTED]

- For eGFR, the categories will be Severe = <30 mL/min/1.73m²; Moderate = ≥ 30 to <60 mL/min/1.73m²; Mild = ≥ 60 to <90 mL/min/1.73m²; and Normal = ≥ 90 mL/min/1.73m².

[REDACTED]

The baseline and worst post-baseline value will be utilized for the shift tables. Note that the shift table dealing with the fasting glucose parameter will require the lab sample to be taken while fasting. Samples taken while the participant was not fasting will not be analyzed.

New onset of diabetes during the study will be identified by evaluating different components:

1) adverse events, [REDACTED]
[REDACTED] 3) initiation of antidiabetic medication. This analysis will only be conducted in participants who do not have diabetes at baseline (determined by either targeted medical history, prior concomitant therapies, [REDACTED] and fasting plasma glucose). Additionally, new onset or worsening of diabetes will be identified using SMQ and AE terms for diabetic treatment emergent adverse events (TEAEs). The analysis will be performed for all participants and then by baseline diabetes status.

A participant will be identified as being diabetic at baseline if ANY of the following conditions are met:

- Targeted medical history of diabetes (using targeted medical history CRF).
- Anti-diabetic medication (ATC level 2 code: A10) at baseline.
- [REDACTED] AND fasting glucose ≥ 126 mg/dL at baseline.

For this analysis, baseline fasting glucose uses the average of the last two assessments measured under fasting conditions at or prior to baseline. If only one fasting glucose value is available at or prior to baseline, the analysis will be based on the available data.

New onset or worsening of diabetes is defined if ANY of the following conditions [REDACTED]

- Laboratory results indicating diabetes, which can be any of the following:
 - The participant has [REDACTED] on two consecutive tests.
 - The participant has fasting glucose ≥ 126 mg/dL on two consecutive fasted tests.
 - The participant has [REDACTED] and fasting glucose ≥ 126 mg/dL on the same occasion.
 - The participant has [REDACTED] on one occasion and has fasting glucose ≥ 126 mg/dL on the succeeding occasion.
 - The participant has fasting glucose ≥ 126 mg/dL on one occasion and has [REDACTED] on the succeeding occasion.
- Diabetic TEAEs identified by the search terms:
 - Hyperglycaemia/new onset diabetes mellitus (SMQ, narrow)
 - Diabetic complications (HLGT)
 - Diabetes mellitus (incl subtypes) (HLT)
 - Carbohydrate tolerance analyses (incl diabetes) (HLT), excluding PT “Blood glucose decreased”
- Initiation of anti-diabetic medication (ATC level 2 code: A10) at any time post-baseline.

The number and percentage of subjects with potentially clinically significant (PCS) laboratory values or clinically significant (CS) laboratory values (refer to Appendix 5.2.2 for the criteria) will be summarized. It is possible that some laboratory values for a parameter may be classified as PCS while others are CS. In this case, the CS laboratory value for that parameter will be used in the summaries. For AST, ALT and CK, the most severe result for each subject will be used. For creatinine, the following two categories will also be presented in addition to the CS criterion:

- 1) Subjects with the baseline value ≤ 2 mg/dL and any post-baseline value > 2 mg/dL.
- 2) Subjects who are not in the first category but has $\geq 50\%$ increase from baseline.

For liver chemistry parameters (ALT, AST, ALP, TBIL), the number and percentage of subjects whose PCS/CS value returned to baseline level at the last measurement will also be summarized. Here the baseline level is defined as a value of the same category as the baseline category or a value of a better category than the baseline. For example, if a subject’s baseline ALT is >3 and ≤ 5 x ULN and the subject’s ALT elevated to >5 and ≤ 10 x ULN at the worst measurement post baseline, the subject is considered to have returned to baseline level at the last measurement if the last ALT value of that subject is ≤ 5 x ULN.

Listings of all subjects with PCS or CS laboratory values will be presented. Subjects will appear once per lab parameter but may appear under multiple lab parameters.

The number and percentage of participants satisfying Hy's Law will also be tabulated by treatment group based on the following lab findings:

- Any elevated post-baseline aminotransferases defined as:
 - ALT > 3 x ULN or
 - AST > 3 x ULN
- Elevated post-baseline serum total bilirubin (TBL) > 2 x ULN and serum alkaline phosphatase (ALP) levels < 2 x ULN

Participants must meet all of the criteria listed above at the same time point and have normal lab variables (ALT, AST, TBL) at baseline to be considered a Hy's Law case. The same analysis will be performed excluding the normal baseline value requirement.

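### SAP 2.7.3 needs two laboratory criteria together for diabetes at baseline but accepts either one alone after baseline, so an unchanged, isolated raised marker is counted as new-onset diabetes

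*SAP*

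**What the plan says.** All the rules are in SAP 2.7.3.

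- **Who enters the new-onset analysis.** "This analysis will only be conducted in participants who do not have diabetes at baseline".
- **Diabetes at baseline.** "A participant will be identified as being diabetic at baseline if ANY of the following conditions are met": a targeted history of diabetes, an antidiabetic drug (ATC A10), or a laboratory rule. The start of the laboratory rule is blacked out and it ends "AND fasting glucose ≥ 126 mg/dL at baseline". As printed, both laboratory parts are needed.
- **Baseline glucose value.** The "baseline fasting glucose uses the average of the last two assessments measured under fasting conditions at or prior to baseline". If only one value exists, that value is used.
- **Who is a case.** "New onset or worsening of diabetes is defined if ANY of the following conditions", after which the sentence is blacked out. The conditions that follow are laboratory results, diabetic adverse event terms, or starting an A10 drug.
- **Laboratory evidence.** "Laboratory results indicating diabetes, which can be any of the following", followed by five patterns. One is "The participant has fasting glucose ≥ 126 mg/dL on two consecutive fasted tests". Another is the blacked-out criterion on two consecutive tests. The other three combine the two markers, on the same or successive occasions.
- **Presentation.** For new onset or worsening, "The analysis will be performed for all participants and then by baseline diabetes status".

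**The concern.** A strict rule decides who is at risk of new-onset diabetes, and a looser one decides who has become a case. Anyone between the two rules at baseline is placed in the at-risk group and can then become a case by staying the same. Prevalent dysglycaemia would be reported as incident diabetes.

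Showing results by baseline diabetes status does not correct this, because the strict rule defines the non-diabetic stratum. In that stratum, a composite labelled new onset or worsening can only be read as new onset.

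The SAP guards against this elsewhere. In SAP 5.2.2, a notable laboratory abnormality generally counts only if the baseline value did not already meet the threshold. The Hy's Law tabulation in SAP 2.7.3 requires normal baseline ALT, AST and bilirubin, with a second version that drops the requirement. No such condition is visible for the laboratory part of the diabetes composite.

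**Working it through.** The documents give no figure for this point, so there is none to reproduce. The check has two parts.

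**1. Logic, from the visible text only.** Take a participant with no history and no A10 drug. Let G mean fasting glucose at or above 126 mg/dL and R mean the blacked-out criterion is met, each held constant at every visit. The laboratory rule at baseline is R and G. After baseline it is R alone, G alone, or a combination.

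| R | G | Diabetic at baseline | Post-baseline rule met | Counted as new onset, unchanged |
|---|---|---|---|---|
| no | no | no | no | no |
| no | yes | no | yes | **yes** |
| yes | no | no | yes | **yes** |
| yes | yes | yes | yes | no (outside the set) |

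Two of four constant states are miscounted. The glucose row does not depend on the hidden threshold. The mirror row assumes that the hidden marker and cut-off are the same before and after baseline.

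**2. How often a stable participant would trigger the glucose pattern.** Protocol Table 8-1 and section 8.4.1.3 put fasting glucose in the chemistry panels at all six visits: two at or before baseline (screening, Day 0) and four after (Days 90, 180, 270, 330). The following are assumptions, not taken from the documents: a stable true level, independent normal within-person variation with CV 5% to 10%, all tests done, and the hidden marker below its threshold throughout.

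Let p be the chance that one value is at least 126, and q = 1 − p. The chance of at least one consecutive pair in four tests is

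1 − q⁴ − 4pq³ − 3p²q².

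Example, true level 130 and CV 5%: SD = 6.5, z = (126 − 130)/6.5 = −0.615, p = 0.731, q = 0.269. The result is 1 − 0.005 − 0.057 − 0.116 = 0.82.

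The next table adds the chance that the pair occurs and the two-value baseline mean was also at least 126. The difference is what would still be counted if a baseline mean below 126 were required.

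| True level (mg/dL) | CV | Pair occurs (as written) | Pair occurs and baseline mean ≥126 | Still counted with baseline mean <126 |
|---|---|---|---|---|
| 120 | 5% | 0.07 | 0.01 | 0.06 |
| 120 | 10% | 0.23 | 0.05 | 0.18 |
| 126 | 5–10% | 0.50 | 0.25 | 0.25 |
| 130 | 5% | 0.82 | 0.66 | 0.16 |
| 130 | 8% | 0.72 | 0.51 | 0.21 |
| 130 | 10% | 0.68 | 0.45 | 0.23 |
| 140 | 5% | 1.00 | 1.00 | 0.00 |
| 140 | 8% | 0.97 | 0.93 | 0.04 |
| 140 | 10% | 0.93 | 0.86 | 0.07 |

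A stable participant above the threshold is therefore usually counted as written, and much less often once the baseline condition is added. Below or at the threshold, much of the miscounting is within-person noise that the baseline condition does not remove.

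**The case against.** The case against giving this much weight has five parts.

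- **It is not the adverse event of special interest.** A reader might infer that the rule distorts that table. SAP 2.7.1.1 defines the diabetes item by MedDRA terms only, and no laboratory value enters it. This part stands.
- **No between-arm ratio is at stake.** A reader might infer that a planned comparison is pulled towards no effect. SAP 2.7.1 plans risk ratios for common, serious and withdrawal-related events. None is visible for the 2.7.3 composite. The rule is the same in both randomised arms, and if stable cases add equally to each, the risk difference is noisier but not biased. This stands too.
- **Other outputs would show unchanged glucose.** SAP 2.7.3 also plans fasting glucose by visit, change from baseline, and a baseline-to-worst shift table. The adverse event and drug-initiation components do not use the glucose threshold. So the documents do not support saying that a glycaemic signal would be lost. They do support saying that the composite's laboratory count is wrong as an incidence.
- **Text is blacked out.** The sentence that governs the post-baseline conditions is cut off, and a limiter could sit there. None appears in the conditions that can be read. The visible asymmetry is certain. That the operative rule has no guard is likely, not proven.
- **Some miscounting is threshold noise.** The table above bears this out near 126 mg/dL. It limits what any baseline condition can achieve, but does not explain away persistently raised values.

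**Conclusion.** The point holds for the laboratory component of the new-onset or worsening composite in SAP 2.7.3. On the visible text, a participant with no history, no A10 drug and one persistently raised marker is non-diabetic at baseline and a new-onset case afterwards without any change. The effect is to inflate that component in both arms.

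The size is limited. This is a descriptive safety summary, and no primary or secondary efficacy analysis depends on it. It is tempting to put a number on the false cases, but that needs the share of participants with an isolated raised marker at baseline, the number without diabetes and their true glucose levels. The documents give none of these, so no count is offered. The probabilities above rest on the assumed CV and true levels. The conclusion also depends on there being no limiting phrase in the blacked-out text.

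**What to change.** In SAP 2.7.3, for the laboratory component only:

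1. Count new onset only when the marker that triggers it was below its threshold at baseline. For glucose, use the SAP's existing baseline value: the average of the last two fasting values, or the single available value, below 126 mg/dL. Apply the same condition to the blacked-out marker.
2. State that the qualifying tests must all be post-baseline. The visible wording does not say so.
3. Report participants with one isolated raised marker at baseline as a separate category. This also settles how to present those who later meet a pattern combining both markers.

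The averaged value is preferable to requiring both baseline values to be at least 126. At a true level of 130 with CV 5%, both values qualify with probability 0.731² = 0.53, so 0.82 × 0.47, about 0.38, would still be miscounted, against 0.16 with the average. A two-value rule also cannot be applied when only one baseline value exists.

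The cost is SAP wording and a baseline flag; fasting glucose is already collected at screening and Day 0. The drawbacks are that some participants, probably few, leave the laboratory new-onset denominator, and that some misclassification near the threshold remains.

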#### 8.4.4.3 Hyperglycemia-related events

Laboratory results and newly added concomitant medications should be checked for potential hyperglycemia-related AEs.

‘New onset of diabetes’ should be reported as AE on the eCRF in participants with no medical history of diabetes when:

█ [REDACTED]

- If a new concomitant medication for control of plasma glucose is added, further information to assess for a diagnosis of new onset diabetes will need to be collected

‘Worsening of glycemic control’ should be reported as AE on the eCRF in participants with a medical history of diabetes ( [REDACTED] ) when:

█ [REDACTED]

- New concomitant medication or increase in dose of current antidiabetic therapy is initiated to improve the control of plasma glucose level

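### In participants without diabetes, SAP 2.7.3 counts the start of any ATC A10 drug as new-onset diabetes, although Protocol 8.4.4.3 asks for a glucose-control purpose and an assessment of the diagnosis

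*SAP*

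**What the plan says.** SAP 2.7.3 first describes a new-onset analysis built from components: adverse events, a blacked-out second item and "3) initiation of antidiabetic medication". Its population is restricted: "This analysis will only be conducted in participants who do not have diabetes at baseline".

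The section then gives the combined rule: "New onset or worsening of diabetes is defined if ANY of the following conditions" (the rest of that sentence is redacted). The conditions are laboratory results, coded adverse event terms, and "Initiation of anti-diabetic medication (ATC level 2 code: A10) at any time post-baseline". On presentation it says: "The analysis will be performed for all participants and then by baseline diabetes status".

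A participant is classed as diabetic at baseline by any one of three conditions, one of which is "Anti-diabetic medication (ATC level 2 code: A10) at baseline".

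Protocol 8.4.4.3 sets the adverse event reporting rules. For participants with no history of diabetes it reads "If a new concomitant medication for control of plasma glucose is added, further information to assess for a diagnosis of new onset diabetes", and goes on to say that this information must be collected. For participants with a history, a new drug or a dose increase is reportable as worsening when it "is initiated to improve the control of plasma glucose level".

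**The concern.** ATC A10 identifies a drug class. It does not say why the drug was prescribed. The protocol makes purpose a condition and, without a diabetes history, does not treat the start itself as an event. The SAP drops both elements, so a single medication record is enough to make a participant without diabetes a new-onset case.

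Everyone in the trial has ASCVD. Only NYHA class III or IV heart failure (or an ejection fraction below 30%) is excluded, and eGFR need only exceed 30 mL/min. I assume that in such a population some A10 drugs may be started for reasons other than glucose; the documents neither say this nor give a rate. Medication records may also come from health-record mapping (Protocol 6.2.1) or linked claims (Protocol 11.1), so an A10 record could enter the derivation without the investigator's assessment. At stake is whether the reported incidence of new-onset diabetes means what its label says.

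**Working it through.** The documents give no diabetes event rate, so there is no planned figure to reproduce. The check is a comparison of texts, followed by an illustration.

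**1. The two rules side by side, for a participant without diabetes**

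| | Protocol 8.4.4.3 | SAP 2.7.3 |
|---|---|---|
| Purpose of the drug | Must be glucose control | Not considered |
| Effect of starting it | Prompts collection of information for a diagnosis | Is itself a case |
| Further evidence | Diagnostic assessment | None |

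**2. The SAP's other conditions.** The visible fasting-glucose criterion needs 126 mg/dL or more on two consecutive fasted tests, or agreement with a second (redacted) criterion on the same or the adjacent occasion. The adverse event search removes the preferred term for decreased blood glucose. Only the medication condition rests on one record with no supporting evidence.

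**3. Where the medication condition reaches.** SAP 2.7.1.1 defines the special-interest category for diabetes by MedDRA terms alone, so A10 starts cannot enter it. SAP 2.7.1 plans risk ratios for common TEAEs, serious TEAEs and TEAEs leading to withdrawal of study treatment, and none for the 2.7.3 composite. The effect is confined to the derived summary.

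**4. Illustration of size.** From the documents: 222 participants per group (Protocol 6.1.3). Assumed, with no source in the documents: 50 to 70% without diabetes at baseline; true new-onset risk t of 2% or 5%; A10 starts for other reasons at rate f of 0 to 5%, independent of true onset.

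- Participants without diabetes per arm: 222 × 0.50 = 111 to 222 × 0.70 = 155.4.
- A10 starts for other reasons per arm: none at f = 0; 111 × 0.01 = 1.1 at the low non-zero end; 155.4 × 0.05 = 7.8 at the high end. Slightly fewer become false cases, because a fraction t are true cases already.
- Counted risk = t + (1 − t)f. False share of counted cases = (1 − t)f / [t + (1 − t)f].

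| t | f | Counted risk | False share |
|---|---|---|---|
| 2% | 0% | 2.00% | 0% |
| 2% | 1% | 2.98% | 33% |
| 2% | 3% | 4.94% | 60% |
| 2% | 5% | 6.90% | 71% |
| 5% | 0% | 5.00% | 0% |
| 5% | 1% | 5.95% | 16% |
| 5% | 3% | 7.85% | 36% |
| 5% | 5% | 9.75% | 49% |

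**5. Effect on a comparison of arms, if someone made one.** Assume true risks of 5% and 3% (ratio 1.67, difference 2.00 points) and f = 4% in both arms. Counted risks are 0.05 + 0.95 × 0.04 = 8.80% and 0.03 + 0.97 × 0.04 = 6.88%. The ratio falls to 8.80/6.88 = 1.28. The difference is 8.80 − 6.88 = 1.92 points, since it shrinks only by the factor 1 − f.

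**The case against.** The best defence is that the two texts do different jobs. Protocol 8.4.4.3 tells investigators what to report as an adverse event. SAP 2.7.3 is a derived screen over adverse events, laboratory data and medication, and a screen may reasonably favour sensitivity. An ATC code is objective, whereas judging the reason for a prescription brings case-by-case judgement into an open-label trial. No document confirms that a reason for use is recorded, so demanding one could lose true cases. Redactions also prevent a full comparison: the end of the SAP's combining sentence, its second component and part of the protocol's criteria are blacked out.

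Much of this stands. The mismatch is an unreconciled definition, not a breach of an analysis rule in the protocol. The practical existence of the problem, as well as its size, depends on A10 drugs being started for other reasons. The worries about missing reasons and open-label judgement should shape the remedy.

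The defence does not remove the point. The medication condition is fully visible and unqualified, and the output is labelled as diabetes, not as a screen. SAP section 4 records departures as small as dropping the interquartile range but does not record this one.

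**Conclusion.** The point holds as a minor one about a descriptive safety summary. In participants without baseline diabetes, an A10 start alone makes a case in SAP 2.7.3, and starts for other reasons would overstate incidence. The direction follows from the rule. The size is unknown, and the figures above depend wholly on assumed rates. No primary or secondary efficacy endpoint, significance level or sample size is affected.

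A reader might infer three stronger things that the documents do not support:

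- **That an adverse event of special interest is inflated.** SAP 2.7.1.1 builds that category from MedDRA terms and has no medication condition.
- **That a planned treatment contrast is pulled towards no difference.** No ratio or test is specified for this composite. The fall from 1.67 to 1.28 needs an unplanned ratio and an equal f in both arms; the risk difference hardly moves.
- **That the baseline A10 rule contradicts the protocol or removes participants from view.** The protocol wording concerns drugs added or increased during the study. Baseline A10 users leave the new-onset analysis but are still reported in the baseline-diabetes stratum. This is a secondary matter.

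**What to change.** Amend SAP 2.7.3 for participants without baseline diabetes:

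- Count an A10 start in the composite when the recorded purpose is glucose control, or when the information collected under Protocol 8.4.4.3 supports diabetes.
- Keep starts with an unknown reason in the composite, so that true cases are not lost where the reason was not captured.
- Show A10 starts for other reasons in a separate row outside the composite.
- Present the composite with and without A10-only cases, meaning those with no supporting laboratory, adverse event or diagnostic evidence.
- List the departure from Protocol 8.4.4.3 in SAP section 4.

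The cost is a change of SAP wording, an extra row and one repeated summary, and a short review of A10 records before database lock. That review should be done without reference to treatment arm, because the trial is open-label. If few reasons were recorded, most starts will stay in the composite, and the version without A10-only cases will then be the main guide to how much they matter.
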